7.4 SERIOUS ADVERSE EVENTS AND UNEXPECTED ADVERSE EVENTS

In addition to the severity rating, each AE is to be classified by the Investigator as “serious” or “not serious.” The seriousness of an event is defined according to the applicable regulations and generally refers to the outcome of an event. An SAE is one that meets one or more of the following:

- Is fatal
- Is life-threatening
- Is persistent or significantly incapacitating or causes substantial disruption of the ability to conduct normal life functions
- Requires inpatient hospitalization
- Prolongs existing hospitalization
- Is a congenital anomaly or birth defect
- Is an important medical event that may jeopardize the subject and may require medical or surgical intervention to prevent one of the outcomes listed above

Definition of Life-threatening

An AE or suspected adverse reaction is considered "life-threatening" if, in the view of either the Investigator or Sponsor (and/or designee), its occurrence places the subject at immediate risk of death. It does not include an AE or suspected adverse reaction that, had it occurred in a more severe form, might have caused death.

Definition of Hospitalization

Hospitalization is defined by the Sponsor as a full admission to the hospital for diagnosis and treatment. This includes prolongation of an existing inpatient hospitalization. Hospitalization may include social hospitalization, defined as inadequate family support/care at subject's primary residence, which results in subject being admitted to the hospital (i.e. wound care, nutrition, etc.).

Examples of visits to a hospital facility that do not meet the serious criteria for hospitalization include:

- Emergency room visits that last for a period of <24 hours and do not result in a full hospital admission
- Outpatient surgery
- Preplanned or elective procedures (Section 7.4.1)
- Protocol procedures

The above events would not be reported as SAEs unless the event triggering the hospital visit is an SAE as defined by other SAE criteria such as life-threatening, results in persistent or significant disability/incapacity or as per medical judgment of Investigator.

Any other event fulfilling the definition of serious that develops as a result of the in-hospital procedure or extends the hospital stay is an SAE.

Definition of Disability

Disability is defined as a persistent or significant incapacity or substantial disruption of the ability to conduct normal life functions.

Definition of Medically Significant

Important medical events (medically significant events) that may not result in death, be life-threatening or require hospitalization may be considered to be an SAE when, based upon appropriate medical judgment, they may jeopardize the subject or may require medical or surgical intervention to prevent one of the outcomes listed in this definition. Examples of such events are intensive treatment in an emergency room or at home for allergic bronchospasm, blood dyscrasias, or convulsions that do not result in hospitalization, or development of drug dependency or drug abuse.

An SAE may also include any other event that the Investigator or medical monitor judges to be serious, or that suggests a significant hazard, contraindication, side effect, or precaution.

Definition of Unexpected AEs or Unexpected Suspected Adverse Reactions

An AE or suspected adverse reaction is considered “unexpected” if it is not listed in the Investigator Brochure or is not listed at the specificity or severity that has been observed. “Unexpected,” as used in this definition, also refers to AEs or suspected adverse reactions that are mentioned in the Investigator Brochure as occurring with a class of drugs or as anticipated from the pharmacological properties of the drug, but are not specifically mentioned as occurring with the particular drug under investigation.

7.4.1 Elective Procedures and Surgeries

For the purposes of this protocol, the following conventions will apply for SAE reporting of elective procedures, and surgeries:

A prescheduled elective procedure or a routinely scheduled treatment is not to be considered an SAE, even if the subject is hospitalized, provided the site stipulates that:

- The condition requiring the prescheduled elective procedure or routinely scheduled treatment was present before and did not worsen or progress between the subject’s consent to participate in the clinical trial and the time of the procedure or treatment
- The prescheduled elective procedure or routinely scheduled treatment is the sole reason for admission and intervention

An untoward medical event occurring during the prescheduled elective procedure or routinely scheduled treatment should be recorded as an AE or a SAE. Any concurrent medications should also be recorded on the eCRF.

7.4.2 Other Reportable Information

In addition, and for the purposes of monitoring, the following should be reported via the SAE form, regardless of seriousness, according to the directions in Section 7.4.4:

- A new diagnosis of cancer
- Any occurrence of pregnancy (with or without AEs)

Note: Any subject who becomes pregnant during the study must be withdrawn from treatment, and will be followed to term. A Pregnancy Follow-up Form may be used to obtain information on the outcome of the pregnancy/status of the infant.

7.4.3 Disease Progression and Death

Disease progression (including progression of hematologic condition and/or organ dysfunction of AL amyloidosis, and death due to disease progression) is generally recorded as part of the efficacy evaluation and should not be reported as a specific AE or SAE. When an AE resulting from disease progression meets the requirements to be considered serious, the SAE verbatim term should be reported as the sign/symptom that best describes the event rather than as “disease progression.” For instance, a subject with pleural effusion presents with shortness of breath. The cause of the shortness of breath is a pleural effusion resulting from disease progression. The event term may be reported as “pleural effusion” instead of disease progression.

Death should not be reported as an SAE, but as a clinical outcome of a specific SAE. The cause of death, reported on a source document such as the Death Certificate or autopsy report, should be used as the event term for the SAE. For example, in a subject with acute heart failure that results in death, the SAE is reported as “acute heart failure” with an outcome of “death.”

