1.2 STUDY RATIONALE

[figure not shown]
Unlike other hematologic disorders such as multiple myeloma, the morbidity and mortality of AL amyloidosis is almost entirely related to organ dysfunction and not hematologic parameters. One of the major determinants of prognostic outcome in AL amyloidosis patients is the extent of cardiac involvement; 75% of the deaths are due to cardiac amyloidosis (Merlini et al, 2011). The process of amyloid formation results in cellular injury, tissue damage, and organ dysfunction through mechanisms that are not completely understood. Because the current available treatment options are limited to treatment for the PCD component of the disease, the rate of organ function improvement or stabilization (“organ response”) after achieving hematologic response from chemotherapy regimens is highly variable, ranging from 25% to 78% based on published information (Cibeira et al, 2011; Cohen et al, 2007; Michael et al, 2010). Furthermore, the incidence of treatment-related mortality following high dose melphalan and ASCT was 13% within the first 100 days in patients with AL amyloidosis (Skinner et al, 2004) and with the greatest mortality in patients with cardiac involvement. Though the ASCT approach is effective and results in rapid hematologic response, the average treatment-related mortality in four single-center studies ranged from 21% to 39% (Falk and Dubrey, 2010). Therefore, there is an urgent need to develop a treatment that can directly target the misfolded proteins to increase their clearance and to alleviate direct organ toxicity. Treatments that reduce or eliminate PCD in conjunction with treatments that target toxic soluble aggregates and insoluble amyloid may be of great clinical benefit in the treatment of AL amyloidosis.

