6.4 PHARMACOKINETIC AND IMMUNOGENICITY ASSESSMENTS

All subjects enrolled in the study will undergo sparse sampling for serum NEOD001 according to [Table 1](#). Serum NEOD001 concentrations from this study will be pooled with similar samples from other studies in a population PK analysis. Details will be provided in a separate document.

Serum anti-NEOD001 antibody levels will be measured according to [Table 1](#). An electrochemiluminescent assay will be used to detect serum anti-NEOD001 antibodies. Any screening positives will be run at increasing dilutions to and a titer determined (expressed as the reciprocal of the dilution that generates a positive response). Additionally, all positives will be run in a confirmatory assay to determine the response is specific to NEOD001.

Additional samples for anti-NEOD001 antibodies and serum NEOD001 should be collected if a significant toxicity is observed (e.g., an infusion reaction in the clinic, anaphylaxis, etc.) and if possible, should be collected while the acute symptoms persist.

Refer to the Laboratory Manual for additional details.

7 **ADVERSE EVENTS/SERIOUS ADVERSE EVENTS AND REPORTING**

7.1 **ADVERSE EVENTS—DEFINITION**

An AE is any untoward medical occurrence associated with the use of a drug in humans, whether or not considered drug related. An AE can therefore be any unfavorable and unintended sign (including a laboratory finding, for example), symptom, syndrome, or disease temporally associated with the use of a medicinal product, whether or not considered related to the medicinal product. Examples include:

- Any treatment-emergent signs and symptoms (events that are marked by a change from the subject's baseline/entry status [e.g., an increase in severity or frequency of preexisting abnormality or disorder])
- All reactions from study drug, abuse of drug, withdrawal phenomena, sensitivity, or toxicity to study drug
- Apparently unrelated illnesses
- Injury or accidents
- Exacerbations of the underlying disease (indication)
- Extensions or exacerbations or symptomatology, subjective events reported by the subject, new clinically significant abnormalities in clinical laboratory, physiological testing, or physical examination

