2.3.3.1. Time to Event Endpoints

- Time to all-cause mortality from first infusion of study drug in the original parent study (NEOD001-001)
- Cardiac progression-free survival from first infusion of study drug in the original parent study (NEOD001-001)

- Time to derived organ progression from first infusion of study drug in the original parent study (NEOD001-001), and from first OLE NEOD001 infusion of study drug
- Time to first organ response from first infusion of study drug in the original parent study (NEOD001-001), and from first OLE NEOD001 infusion of study drug
- Duration of organ response from first derived organ response

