8. EFFICACY ANALYSES

All recorded efficacy endpoint data will be presented in by-subject data listings for the OLE Safety Population. No summary tables or figures will be produced for the efficacy endpoints.

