9.2.7. Serious Adverse Events and Deaths

The crude incidences of serious TEAEs will be summarized. The incidence of fatal TEAEs will be summarized separately. In addition, the cumulative incidences of serious TEAEs and deaths will be summarized. The following summaries will be presented:

- Subject incidence of serious TEAEs by MedDRA SOC and PT
- Subject incidence of serious related TEAEs by MedDRA SOC and PT
- Subject incidence of fatal TEAEs by MedDRA SOC and PT

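### Protocol 7.4.3 is inconsistent on deaths from AL progression, and no SAP safety table is assured to count all deaths

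*Protocol*

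**What the plan says.** **Reporting rules in the protocol**

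- Section 7.4.3, first sentence: progression of AL amyloidosis, including death due to it, "is generally recorded as part of the efficacy evaluation and should not be reported as a specific AE or SAE".
- Section 7.4.3, next sentence: when an AE resulting from progression is serious, "the SAE verbatim term should be reported as the sign/symptom that best describes the event rather than as" disease progression.
- Section 7.4.3, second paragraph: "Death should not be reported as an SAE, but as a clinical outcome of a specific SAE". The cause of death becomes the event term; the worked example is a death from acute heart failure.
- Section 7.1 gives as an example of an AE "Exacerbations of the underlying disease (indication"). Section 7.4 lists a fatal outcome among the criteria for an SAE.
- Section 8.3 promises a listing and summary of SAEs, deaths among them.

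**Outputs in the SAP**

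- Section 9.2 restricts all AE summaries to TEAEs, up to 30 days after the last dose or the last study visit, whichever is later.
- Section 9.2.2 identifies a fatal TEAE by a fatal outcome or CTCAE Grade 5 on an AE record.
- Section 9.2.7 promises cumulative incidences of serious TEAEs and of deaths, but the only death output it itemises is "Subject incidence of fatal TEAEs by MedDRA SOC and PT".
- Section 2.3.3.1 classes survival as exploratory efficacy: "Time to all-cause mortality from first infusion of study drug in the original parent study (NEOD001-001"). For that class, section 8 states: "No summary tables or figures will be produced for the efficacy endpoints". The protocol (8.4) had planned a Kaplan-Meier summary; SAP 11 declares the change and gives discontinuation of the program as the reason.

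**The concern.** This is an uncontrolled long-term safety study, and the frequency and severity of AEs is a primary endpoint. Deaths are the most serious events it can record. If a death reaches a safety table only when the site has opened an AE record for it, the count depends on whether the site attributes the death to the drug, to another illness or to the amyloidosis. The first sentence of 7.4.3 tells sites that the last of these belongs to efficacy, and the SAP now gives efficacy no summaries. Two sites could handle the same cardiac death differently and both could point to the protocol. With no control group, nothing in the data would reveal the difference.

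**Working it through.** The plan states no figure on this point, so there is none to reproduce. The check follows a death through the reporting rules and the planned outputs, then compares two time windows.

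**Step 1. The instruction to the site.** The second paragraph of 7.4.3 needs a specific SAE to which the fatal outcome can be attached. For a death from progression, the first sentence says that the progression, and the death due to it, should not be such an event. The middle sentence supplies an SAE under a sign or symptom, and 7.1 and 7.4 support that. Nothing says which sentence governs when the death is itself the progression event. The passages allow two readings: a naming rule (report it, but under another term) or an exclusion (leave it to efficacy).

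**Step 2. Where each kind of death would be counted.**

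| Death | Fatal TEAE tables (SAP 9.2.2, 9.2.7) | Cumulative incidence of deaths (SAP 9.2.7) | Disposition (SAP 7.1) | Efficacy listing (SAP 8) |
|---|---|---|---|---|
| A. In the TEAE window, reported as a fatal SAE | Yes | Yes | Depends on eCRF reasons | Yes |
| B. In the window, recorded only as efficacy | No: no AE record | Not stated | Depends on eCRF reasons | Yes |
| C. After the window, found by a vital status call | No: outside the window | Not stated | Not after a completed EOS Visit | Yes |

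The entry *not stated* arises because SAP 9.2.7 does not define deaths, while SAP 9.2.1.2 bases cumulative incidence on TEAEs and computes it by SOC and PT. Read with its own method section, the summary covers fatal TEAEs only. Read by its wording alone, it could cover all deaths. Protocol 8.3 does not settle rows B and C, because it treats deaths as a subset of SAEs.

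Rows B and C have different causes. B follows from 7.4.3. C follows from the TEAE window and would remain if 7.4.3 were perfectly clear. After the reporting period, Protocol 7.4.4 asks for an SAE report only where the investigator sees a reasonable possibility that the product caused the event.

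**Step 3. Length of the two windows.** Inputs: 36 infusions 28 days apart (Protocol 6.1.2); EOS Visit 30 (±5) days after the last dose (6.1.3); vital status calls for up to 5 years (6.1.5), assumed to run from the last study visit; 30.4375 days per month (SAP 4.5).

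- Last infusion: 1 + 35 × 28 = Day 981.
- End of TEAE window: 981 + 30 = Day 1011, or 981 + 35 = Day 1016 with a late EOS Visit. That is 1011 / 30.4375 = 33.2 months, or 1016 / 30.4375 = 33.4 months.
- End of vital status calls: 1011 + 5 × 365.25 = Day 2837.25, or 93.2 months. With the late EOS Visit it is Day 2842.25, or 93.4 months.
- Share of the collection period inside the window: 1011 / 2837.25 = 0.356, or 1016 / 2842.25 = 0.357, about 36%.

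This is a share of time for a treatment completer followed for the full 5 years. It is not a share of deaths. It falls for a subject who stops treatment early and rises if the calls end early.

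**The case against.** The best defence is that 7.4.3, read whole, is a naming convention. Its first sentence is softened by *generally*; the next sends serious consequences of progression through SAE reporting; the rule on deaths has no exemption for progression, and its worked example is a heart-failure death reported as a fatal SAE. On that reading most progression deaths would be reported under another term. SAP 9.2.7 does name a summary of deaths apart from fatal TEAEs. The eCRF reasons for withdrawal are not in the documents and may include death. With approximately 70 subjects at most, deaths could be counted from the listings.

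Much of this stands, and it rules out three stronger readings that a reader might draw.

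- *Progression deaths are excluded from safety reporting and appear in no table.* The documents support an unreconciled instruction and an undefined term. They do not support a clean exclusion.
- *The loss can be sized from the protocol's statement that "75% of the deaths are due to cardiac amyloidosis".* That is a cited figure for the disease in general. It is not the share of deaths that sites would leave unreported, and neither document gives a death count for this study.
- *The Kaplan-Meier summary must be restored.* Survival is exploratory, and SAP 11 declares the change with its reason.

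What the defence does not supply is a rule a site can follow without choosing between sentences, or a table specified to count every death. A listing lets a reader count deaths but does not commit the report to a number.

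**Conclusion.** The point holds as a gap in specification. Protocol 7.4.3 conflicts with itself, and its first sentence conflicts with 7.1 and 7.4, on how a death from progression is reported. In the SAP, no safety table is assured to count all deaths: the itemised tables need an AE record inside the TEAE window, the term *deaths* in 9.2.7 is undefined, and all-cause mortality is listing-only. A progression death recorded only as efficacy could be missed, and so could any death after the window.

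The number of deaths affected cannot be derived from the documents and may be small if sites follow the naming-rule reading. The one figure available is the time share of about 36%, which rests on the planned schedule, full treatment and 5 years of calls from the last visit; the discontinuation of the program may change it. The declared reason for dropping efficacy summaries does not reach this point, because death is also a safety outcome in this study.

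**What to change.** 1. **Protocol.** Reconcile 7.4.3 with 7.1 and 7.4 so that the reporting of a progression death within the AE reporting period has one reading, stating whether the first sentence governs only the choice of event term or whether an SAE is reported at all.
2. **SAP 9.2.7.** Define *deaths* as all-cause deaths in the OLE Safety Population, taken from the death and vital status data and independent of AE coding. SAP 4.3 already has date rules that use telephone contacts to establish when a subject was last known alive.
3. **SAP 9.2.7.** Add one table: number of deaths, timing from the last dose (within or after the TEAE window), and cause where recorded. That qualifier is needed because Protocol 4.4 and 6.1.5 speak only of vital or survival status, so cause may be unavailable for deaths found by telephone or in public sources.

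The cost is a protocol clarification and one extra table, with no new data collection. The downside for the sponsor is that the fatal-event count may look less favourable. The SAP changes can be made even though the program has been discontinued.

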7.4.4 Serious Adverse Events—Reporting

It is the responsibility of the Principal Investigator to report SAEs to the Sponsor or its designee within 24 hours.

All SAEs must be reported immediately (within 24 hours of discovery) to the Sponsor or its designee (see Study Manual for details). Do **not** delay in the reporting of a suspected SAE in order to obtain additional information. Any additional information, if collected, can be reported to the Sponsor or its designee as a follow-up to the initial report. SAEs will be reported using the SAE forms provided as part of the Study Manual. Please remember to give details of the study-specific site and subject numbers or other appropriate terminology and ensure the narrative is comprehensive and includes a chronology and assessment of the event.

Reporting of SAEs to the Institutional Review Board/Institutional Ethics Committee (IRB/IEC) will be done in compliance with the standard operating procedures and policies of the IRB/IEC and with applicable regulatory requirements. Adequate information must be obtained by the Sponsor or its designee showing that the IRB/IEC was properly and promptly notified as required.

The process for reporting an SAE, pregnancy or new cancer is as follows:

- Complete the appropriate eCRF(s)
- Complete an SAE form—this must include the subject’s date of birth or age, sex, and study-specific site and subject numbers
- Complete the narrative, which should be comprehensive and include a chronological description and assessment of the event
- Complete the SAE fax cover sheet
- Call the Sponsor Medical Monitor for life-threatening or fatal events (see contact information on Team Roster in Study Manual)

- Fax the cover sheet and the SAE form (within 24 hours of discovery) to the Safety Representative number listed on the Team Roster in the Study Manual

The Investigator is encouraged to discuss any AEs with the Sponsor Medical Monitor for which the issue of seriousness is unclear or questioned. Contact information for the Medical Monitor is listed on the Team Roster in the Study Manual.

The reporting period for SAEs is the period from signing of the ICF through 30 days after the last administration of study drug or last study visit, whichever is later. SAEs reported to the Investigator outside of this reporting period will be reported to the Sponsor or its designee if, in the judgment of the Investigator, there is “a reasonable possibility” that the event may have been caused by the product.

All SAEs will continue to be followed until the end of the study or until such events have resolved or the Investigator, in conjunction with the Sponsor or its designee, deems them to be chronic or stable.

8 **STATISTICAL METHODS AND CONSIDERATIONS**

The final analyses will be based on all subject data collected through study discontinuation.

